The analyses are carried out using linear mixed models. Each model is tested with the car::Anova() function (model comparison Typ II ANOVA) in R to determine the significance of the individual effects. The model equations are written down below and the abbreviations used for the effects are explained.

grp: experimental vs. control group (enters model equation as factor: experimental

group is reference group)

sugg: suggestibility (enters model equation as linear predictor)

a. HIQ ~ grp + sess + grp:sess + (1 | id)

sess: baseline vs. post first session vs. post second session vs. post third session (enters model equation as factor)

For hypothesis a(i) we investigate the significance of sess.

For hypothesis a(ii) we investigate the significance of grp:sess.

b. HIQ ~ grp + sugg + mtp + sugg:mtp + grp:sugg + grp:mtp + grp:sugg:mtp + (1 | id)

mtp: measurement time point, baseline vs. post third session (enters model equation as factor)

For hypothesis d(i) we investigate the significance of sugg:mtp.

For hypothesis d(ii) we investigate the significance of grp:sugg:mtp.

c. HIQ ~ grp + mtp + grp:mtp + (1 | id)

mtp: measurement time point, post third session vs. one-week follow-up (enters model equation as factor)

For hypothesis b we investigate the significance of grp:mtp.

d. fear ~ grp + sugg + sess + rise + rise^2 + grp:sugg + sess:rise + sess:rise^2 + (rise + rise^2 | id)

sess: first session vs. second session vs. third session (enters as linear predictor)

rise: 20 rises during each of the three sessions, these are entered as a centered variable into the model equation (centered at total mean)

For hypothesis c(i) we investigate the significance of rise and rise^2.

For hypothesis c(ii) we investigate the significance of sess.

For hypothesis c(iii) we investigate the significance of sess:rise.

For hypothesis c(iv) we investigate the significance of sess:rise^2.

For hypothesis c(v) we investigate the significance of grp.

For hypothesis d(iii) we investigate the significance of grp:sugg.

4. Sample Size

- a. Analysis a needs 56 participants to achieve a Power of 80% for the effects of interest.

- b. Analysis **b** needs 92 participants to achieve a Power of 80% for the effects of interest.
- c. Analysis **c** needs 60 participants to achieve a Power of 80% for the effects of interest.
- d. Analysis **d** needs 50 participants to achieve a Power of 80% for the effects of interest.

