In order to prevent insufficient Power due to drop-outs, about 10% more participants should be surveyed. A total of 100 participants should therefore be surveyed (50 per group). If it is not possible to survey 100 participants, some of the analyses mentioned above can also be carried out with fewer participants and (as indicated) still enough Power.

5. Exploratory Analyses

- a. Exploratory Relationships:
 - i. More suggestible people report a higher perceived presence in the VR environment than less suggestible people (in both groups).
 - 1. Correlation test (correlation between suggestibility and average experience of presence)
 - ii. More suggestible persons in the experimental group report a higher subjective trance depth than less suggestible persons in the experimental group.
 - 1. Correlation test (correlation between suggestibility and mean trance depth of the experimental group)
- b. Exploratory Analyses:
 - i. We expect a reduction in fear of heights after each session.
 - 1. $\text{HIQ} \sim \text{grp} + \text{mtp} + \text{grp:mtp} + (1 | \text{id})$ (for all sessions)
 - a. mtp: measurement time point, pre vs. post per session
 - ii. We expect that the experimental group shows a lower level of fear of heights in the one-week follow-up than in the pre-measurement of the second session (one-week follow-up after one session). (no investigation of the control group)
 - 1. $\text{HIQ} \sim \text{follow} + (1 | \text{id})$
 - a. follow: pre second session vs. one-week follow-up
 - iii. We also plan to look at how many subjects in the experimental group continue to report a fear of heights below the cut-off for inclusion in the study (HIQ Score > 29) after three months.
- c. Checks:
 - i. We expect no difference in suggestibility between the groups.
 - 1. $\text{sugg} \sim \text{grp} + (1 | \text{id})$
 - ii. We expect no influence of suggestibility on the initial extent of fear of heights
 - 1. $\text{HIQ} \sim \text{sugg} + (1 | \text{id})$
 - iii. We expect no difference in the initial extent of fear of heights between the two groups.
 - 1. $\text{HIQ} \sim \text{grp} + (1 | \text{id})$

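### Model d tests two between-person effects, c(v) and d(iii), without the baseline HIQ the trial already collects: a small missed gain in precision, not a power shortfall

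*SAP*

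**What the plan says.** SAP section 3, analysis d, models the fear ratings given during the height exposure: "fear ~ grp + sugg + sess + rise + rise^2 + grp:sugg + sess:rise + sess:rise^2 + (rise + rise^2 | id". Two of its hypotheses concern differences between people: "For hypothesis c(v) we investigate the significance of grp", and "For hypothesis d(iii) we investigate the significance of grp:sugg".

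The repeated structure is three sessions with twenty ratings each: "rise: 20 rises during each of the three sessions, these are entered as a centered variable into the model equation (centered at total mean").

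Baseline HIQ is measured. In analysis a it is the first level of the session factor: "sess: baseline vs. post first session vs. post second session vs. post third session (enters model equation as factor"). It is also a level of mtp in analysis b. Section 5, checks c.ii and c.iii, examines initial HIQ against suggestibility and group. No model uses it as a covariate.

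Section 4 says of analysis d that it "needs 50 participants to achieve a Power of 80% for the effects of interest". It plans 100 participants, including about 10% for drop-out. If 100 cannot be reached, it says that "some of the analyses mentioned above can also be carried out with fewer participants and (as indicated) still enough Power".

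**The concern.** Within a person, grp and grp:sugg do not vary. Sixty ratings per person average out rating noise but leave the differences between people, and these set the standard errors for c(v) and d(iii). Only more people, or a person-level covariate related to the outcome, can reduce that part.

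Models a, b and c test their group hypotheses as interactions with time, so a stable difference between people drops out of the contrast. Model d has no such safeguard: a chance difference in initial fear goes into grp as noise. Check c.iii shows that the authors thought about baseline balance, but the SAP does not say what follows for model d.

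At stake are wider confidence intervals and somewhat lower power for two hypotheses. The within-person tests, c(i) to c(iv), are not affected.

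**Working it through.** **Inputs from the SAP.** 50 participants for 80% power in analysis d; 100 planned, 50 per group; 3 × 20 = 60 ratings per person; an inclusion cut-off, given in section 5 b.iii ("below the cut-off for inclusion in the study (HIQ Score > 29").

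**Assumptions, not in the SAP.** Two-sided alpha 0.05. r is the within-group correlation of baseline HIQ with a person's mean fear rating among those enrolled, taken from 0 to 0.5.

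**Step 1: the plan's own figure.** The 50 cannot be reproduced, because the SAP gives no alpha, effect size, SD or intraclass correlation. It can be inverted. If it applies to grp with 25 per group, the implied standardized difference in person means is (1.960 + 0.842) × √(2/25) = 0.79.

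**Step 2: do 60 ratings help?** The between-person share of the variance of a person's mean is ICC / [ICC + (1 − ICC)/60]. This is 0.963 at ICC 0.3 and 0.993 at ICC 0.7 (ICC assumed). More ratings hardly help.

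**Step 3: range of r.** The HIQ cut-off narrows the baseline range and may lower r. As an illustration, place the cut at the median of a normal distribution: the SD ratio is u = √(1 − 2/π) = 0.603, and r′ = ρu / √(1 − ρ² + ρ²u²). Then 0.3 becomes 0.19 and 0.5 becomes 0.33. All four values are carried forward.

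**Step 4: net variance factor.** Adjusting multiplies the variance of both effects by v = (1 − r²) × [1 + 1/(N − 6)]. The second factor is the cost of the extra parameter: 1 + 1/44 = 1.0227 at N = 50 and 1 + 1/94 = 1.0106 at N = 100. The excess standard error without the covariate is 1/√v − 1. For r = 0.3 and N = 50, v = 0.91 × 1.0227 = 0.931 and 1/√0.931 − 1 = 3.7%.

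| r | Excess SE, N = 50 | Excess SE, N = 100 | 100 unadjusted equal this many adjusted |
|---|---|---|---|
| 0.19 | 0.7% | 1.3% | 97 |
| 0.30 | 3.7% | 4.3% | 92 |
| 0.33 | 4.8% | 5.4% | 90 |
| 0.50 | 14.2% | 14.9% | 76 |

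Adjustment breaks even where v = 1: r about 0.15 at N = 50 and 0.10 at N = 100.

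**Step 5: simulation of model d itself** (3 sessions × 20 rises, 100 runs per cell, r set on the random intercept). The ratio of the standard error without to that with baseline HIQ, for grp at r = 0.3 and 0.5, was 1.041 and 1.171 at N = 50, and 1.042 and 1.149 at N = 100. For grp:sugg it was 1.047 and 1.168, then 1.043 and 1.149. Monte Carlo error is at most 0.012. This agrees with step 4, with the N = 50, r = 0.5 cells somewhat above it. For sess, sess:rise and sess:rise^2 the ratio was 1.000 throughout.

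**Step 6: power for grp**, from a 1-df noncentral chi-square with noncentrality 7.849 × (N/50) × f² / v. Here 7.849 gives 80% at N = 50, f is the true effect divided by the planned effect, and v = 1 without adjustment. For N = 50, r = 0.3 and f = 1, 7.849/0.931 = 8.43, which gives 82.7%.

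| Case | Unadjusted | r = 0.19 | r = 0.30 | r = 0.33 | r = 0.50 |
|---|---|---|---|---|---|
| N = 50, f = 1 | 80.0% | 80.6% | 82.7% | 83.5% | 89.2% |
| N = 100, f = 1 | 97.7% | 98.0% | 98.5% | 98.7% | 99.5% |
| N = 100, f = 0.6 | 66.2% | 67.3% | 69.8% | 70.7% | 77.9% |

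The last row is illustrative; the SAP says nothing about a smaller effect.

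**The case against.** The strongest reply is that nothing is wrong here. A prespecified unadjusted model is valid, contradicts nothing in the SAP and introduces no bias. By the SAP's own figures the gain is slight: 50 are said to suffice and 100 are planned, so at full recruitment adjustment adds at most about 2 points of power. The stated number covers several effects, so it may be set by another one, with grp better powered than 80%. If grp had 90% at N = 50, the gain at N = 100 would be under half a point. And r is unknown.

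Most of this stands, and it limits the weight of the point. It does not remove it. The covariate is already collected, the cost is one degree of freedom, and settling the choice in advance avoids a decision after the baseline comparison has been seen.

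A reader might infer that analysis d is underpowered, or that the allowance for fewer participants fails. The document does not support either. For analysis d the indicated number is 50, the SAP claims adequate power there, and without its assumptions that claim can be neither confirmed nor refuted.

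A reader might also make much of the three exploratory checks, which carry (1 | id) although each person has one suggestibility score and one initial HIQ. Person and residual variance then cannot be separated. But lme4 stops with an error, and nlme returns the ordinary linear-model estimate; the SAP does not name a package. No wrong result follows and no confirmatory result depends on the checks, so this is only a side remark.

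**Conclusion.** The point holds as a low-severity improvement. Model d forgoes precision on c(v) and d(iii) that baseline HIQ could supply; its other tests are unaffected. For r between 0.19 and 0.5 the excess standard error is 0.7 to 14.2% at N = 50 and 1.3 to 14.9% at N = 100. At 100 participants with the planned effect true, the power consequence is at most about 2 points. The gain matters mainly if the effect is smaller than planned or fewer people are surveyed, which section 4 allows.

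This rests on two-sided alpha 0.05, on an r that the SAP does not give and, for the power figures, on the premise that grp has exactly 80% power at N = 50. Below an r of about 0.15 (N = 50) or 0.10 (N = 100) there is no gain.

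**What to change.** Add baseline HIQ, centred, as a fixed covariate in model d, and state that it is included whatever the checks in section 5c show. No new data are needed. The cost is one line of SAP text and one degree of freedom. If r = 0, the variance of the two effects rises by about 2% at N = 50 (1/44) and 1% at N = 100 (1/94), and under the 80% premise power falls from 80.0% to 79.1% and from 97.7% to 97.6%.

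As housekeeping, drop (1 | id) from the three checks, fit them as ordinary linear models, and report estimates with confidence intervals.

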Preregistration on Clinicaltrials.gov

Project:

„Hypnosis Induction and Height Experience in VR - Control Group Comparison and Three Sessions“

Unique Protocol ID: 521/2019BO2

Description of the Hypotheses, Analyses and needed Sample Sizes

06.05.2024

1. Data collection. Have any data been collected for this study already?

No data has been collected for this study.

2. Hypothesis: What's the main question being asked or hypothesis being tested in this study?

- a. Do three sessions of VR therapy reduce the fear of heights in both groups?
 - i. We expect a decrease in fear of heights over the sessions.
 - ii. Fear of heights decreases over the three sessions, with the experimental group benefiting more from the sessions than the control group.
- b. The fear of heights increases less from after the last therapy session to the follow-up measurement after one week in the experimental group than in the control group.
- c. Does the anxiety experience curve change during the VR height confrontation over the three sessions in both groups?
 - i. We expect typical anxiety experience curves according to the habituation (linear increase in anxiety and quadratic decrease).
 - ii. We expect a decrease of the mean anxiety experience rating over the sessions.
 - iii. We expect that the anxiety experience curves rise less sharply with each session.
 - iv. We expect that the anxiety experience curves reach their turning point earlier with each session.
 - v. The experimental group has lower anxiety experience ratings across all sessions and rises (20 ascents during the height confrontation) compared to the control group.
- d. How does a person's suggestibility influence the perception and impact of the intervention?
 - i. More suggestible people show a greater reduction in anxiety over the three sessions than less suggestible people.
 - ii. The influence of suggestibility on the strength of reduction in anxiety over the three sessions is stronger in the experimental group than in the control group.
 - iii. Suggestibility and group affinity interact such that in the experimental group participants with higher suggestibility show a lower level of anxiety experience during the height confrontation than less suggestible participants, but in the control group higher suggestible participants exhibit greater anxiety experience during the height confrontation than less suggestible participants.

3. Analyses

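### Model d gives each person one curve for all three sessions, so its test of sess for c(ii) rejects too often, at any sample size, if people vary between sessions or ratings are serially correlated within a session

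*SAP*

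**What the plan says.** The SAP, section 3, writes out model d in full. Its interaction and random terms are "sess:rise + sess:rise^2 + (rise + rise^2 | id"), where sess enters as a linear predictor over three sessions. The repeated measure within a session is defined as "rise: 20 rises during each of the three sessions", centred. Each person therefore contributes 3 × 20 = 60 ratings. The model has no by-person sess slope, no person-by-session term, and no fixed grp:sess or sugg:sess.

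Section 2 states c(ii) as "We expect a decrease of the mean anxiety experience rating over the sessions". Section 3 assigns the test: "For hypothesis c(ii) we investigate the significance of sess", by Type II `car::Anova()`. The SAP names no robust standard error, sensitivity model or rule for choosing random effects.

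Section 4 says that analysis d "needs 50 participants to achieve a Power of 80% for the effects of interest". It adds that, if 100 people cannot be surveyed, "some of the analyses mentioned above can also be carried out with fewer participants and (as indicated) still enough Power".

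**The concern.** Hypothesis c(ii) is about change between sessions, so its unit of replication is one person in one session. Model d has nowhere to put a person's good or bad day, or a personal rate of improvement across sessions. Such variation falls into the residual and is averaged over 20 ratings as if it were independent from rise to rise. It is not, and the standard error for sess comes out too small. Serial correlation between successive ratings has the same effect.

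Variation in improvement is plausible on the SAP's own reasoning. Hypothesis d(i) expects that "More suggestible people show a greater reduction in anxiety over the three sessions than less suggestible people", and d(ii) that "The influence of suggestibility on the strength of reduction in anxiety over the three sessions is stronger in the experimental group". Both are tested on HIQ in analysis b, so they say nothing about its size in the fear ratings.

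At stake is a listed hypothesis, not one of the exploratory analyses in section 5: a chance shift between sessions could be declared a change.

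**Working it through.** **The plan's own figure.** The 50 participants for analysis d cannot be reproduced. The SAP gives no alpha, sidedness, effect size, variance components or power method. This does not affect the check below, because N cancels.

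**Inputs from the SAP (section 3, analysis d).** Three sessions, 20 rises per session, sess linear (coded −1, 0, 1 here), rise centred, one random intercept/linear/quadratic curve per person.

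**Assumed.** Two-sided 5% test and complete, balanced data. Residual variance is σ² and person-by-session level variance τ², with r = τ²/σ². The SD of personal session slopes is s, in residual SDs per session.

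**Step 1: variance that model d reports.** Per person, the sum of squares of sess is 20 × (1 + 0 + 1) = 40. The reported variance is σ̂²/(40N).

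**Step 2: true variance.** A session mean has variance τ² + σ²/20. The session trend is (mean 3 − mean 1)/2, so its variance is (τ² + σ²/20)/2 = (σ² + 20τ²)/40 per person, or (σ² + 20τ²)/(40N) overall.

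**Step 3: how much the residual absorbs.** Removing a three-parameter curve from 60 ratings leaves 57 degrees of freedom, and the shifts add 40τ²/57 = 0.70τ². So σ̂² ≈ σ² + 0.70τ².

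**Step 4: variance ratio and error.** True/reported = (1 + 20r)/(1 + 0.70r). True error = 2{1 − Φ(1.96/√ratio)}. N has dropped out.

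| r (assumed) | ratio | true error | simulated, N=50 | simulated, N=100 |
|---|---|---|---|---|
| 0 | 1.00 | 5.0% | 5.3% | 5.0% |
| 0.02 | 1.38 | 9.5% | 9.7% | 9.5% |
| 0.05 | 1.93 | 16% | 18.0% | 16.2% |
| 0.10 | 2.80 | 24% | 25.2% | 24.8% |
| 0.25 | 5.10 | 39% | 38.8% | 38.0% |

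(4000 runs per cell.) The error reaches 10% at r = 0.022.

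**Personal change across sessions instead.** The ratio is (1 + 40s²)/(1 + 0.70s²). At s = 0.10, 0.15 and 0.25 the error is 9.6%, 15% and 28%.

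**Serial correlation alone (AR(1) within session).** At ρ = 0.1, 0.2 and 0.3 the error for sess is 7.6%, 11.0% and 15.1% (ratio 1.50 at ρ = 0.2).

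**Session-varying curve shape alone.** Curvature variance of 0.1 and 0.5 of residual variance (centred rise divided by 10) gives simulated errors for sess from 7.1% to 16.6%. The same variances for the linear within-session slope give 3.8% to 4.8%: no inflation, because rise is centred.

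**Check with fitted models.** With lme4 and Type II `car::Anova()` at N=50, 300 runs each (Monte Carlo SE 1 to 2.5 points), planned model d rejects for sess in 3.3%, 16.7% and 25.3% of runs at r = 0, 0.05 and 0.10. With the two added terms given under the fix, the rates are 2.7%, 5.3% and 6.7%. Both terms are needed: under personal session slopes, a person-by-session intercept alone still leaves 6.6% to 15.3%.

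**c(iii) and c(iv).** Level shifts alone make these tests slightly conservative (4.8% falling to 3.4% as r goes from 0.02 to 0.25). Serial correlation of 0.2 raises sess:rise to 10.2% and sess:rise^2 to 9.5%.

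**The case against.** The strongest objection is that the size is unknown. The SAP gives no variance components, and the expectations in d(i) and d(ii) concern HIQ. That stands: 9.5% to 39% spans an assumed range, not an estimate. But the planned test tolerates very little, since r of about 0.02 nearly doubles the error.

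Those expectations also describe systematic moderation, which fixed sugg:sess and grp:sess terms could absorb. Model d has neither, and they would remove only the part that group and suggestibility explain.

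c(ii) predicts a decrease, so only half of each two-sided rate is false support for it, about 12% at r = 0.10. True, but the nominal rate in that direction is then 2.5%, and the relative inflation is unchanged.

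Stronger readings are tempting, and the document does not support them:

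- *The c(ii) test is wrong as it stands.* It is wrong only under the conditions named. Conversely, absence of session-level variation does not by itself make it right, because serial correlation alone inflates it.
- *c(iii) and c(iv) fail for the same reason.* Level shifts alone do not inflate them. Session-specific or personally trending curve shape, or serial correlation, would.
- *The whole of model d is affected.* c(v) and d(iii) are outside this point.
- *The 50 participants are too few.* The SAP does not say which effect set that number or with what inputs, so no error in it is shown.

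**Conclusion.** The point holds in conditional form and should be fixed. The model is fully written out, its error term for sess ignores the session as a unit, and nothing else in the SAP makes up for it. Given any of the named departures, the direction of the error is certain. Its size depends on quantities that the SAP does not give, and the figures assume a two-sided 5% test with balanced, complete data. Raising the sample from 50 to 100 leaves the error rate where it is.

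**What to change.** **For c(ii).** Replace the random part of model d by `(rise + I(rise^2) | id) + (0 + sess | id) + (1 | id:sess)`, with sess centred.

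**Fallback, pre-specified.** Take each person's mean rating per session and test the person-level session trend of these means. Name the mean explicitly. The intercept of a per-session quadratic fit has 2.26 times the variance, would cut power from 80% to about 45%, and would change the target to fear at mid-session. State how people with fewer than three sessions are handled: one session gives no trend, two give a less precise one, and section 4 allows about 10% for drop-out. With complete data, the fallback's error was 4.4% to 5.9% in simulation. Where the planned test is valid and has 80% power, the fallback has 78.4% at N=50 and 79.2% at N=100. Neither result was checked with missing sessions.

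**If c(iii) and c(iv) are to be protected too.** The c(ii) change does not do this: at ρ = 0.2 it leaves sess:rise at 10.0% and sess:rise^2 at 9.0%. Either test the person-level session trend of the per-session linear and quadratic coefficients, or add id:sess terms for rise and rise^2 together with by-person sess:rise and sess:rise^2 slopes. The id:sess terms alone do not cover a personal trend in curve shape. With an assumed trend SD of 0.03 or 0.05 residual SD per rise per session, sess:rise would still have error of about 9.5% or 12.4%.

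**Sample size.** State whether the 50 participants for analysis d were derived for the session effects.

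**Cost.** SAP wording and code only; section 1 says that no data had been collected. Standard errors for session effects widen where session-level variation exists, and the fuller model for c(iii) and c(iv) may need some convergence work.

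### Model d has no person-by-session error term for the curve-shape tests c(iii) and c(iv), so carry-over between successive ratings would make them reject too often

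*SAP*

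**What the plan says.** SAP section 3, analysis d, models the fear rating with fixed effects for group, suggestibility, session, rise and rise squared, plus selected interactions. The last terms of the formula are "sess:rise + sess:rise^2 + (rise + rise^2 | id". The random part is thus one intercept, slope and quadratic per participant.

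- Ratings: "rise: 20 rises during each of the three sessions, these are entered as a centered variable into the model equation". That gives 3 × 20 = 60 ratings per participant.
- Session coding: "sess: first session vs. second session vs. third session (enters as linear predictor".
- Decision rules: "For hypothesis c(iii) we investigate the significance of sess:rise" and "For hypothesis c(iv) we investigate the significance of sess:rise^2".
- Test: "Each model is tested with the car::Anova() function (model comparison Typ II ANOVA) in R". This uses the fitted model's own standard errors.

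Section 4 says that analysis d "needs 50 participants to achieve a Power of 80% for the effects of interest". The document names no residual correlation, person-by-session random effect, robust variance or sensitivity analysis for this model. It states no significance level.

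**The concern.** The 20 ratings of a session are successive reports of one state, and section 2 itself treats them as an anxiety curve shaped by habituation. A quadratic will not follow every drift in a person's anxiety, so neighbouring ratings may stay alike after the fitted curve is removed. Model d treats them as independent given that curve.

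The participant's random slope and quadratic might seem to absorb this. For main effects of rise they do provide a between-person error term. For sess:rise and sess:rise^2 they do not, because the same curve applies in every session and drops out of any comparison between sessions. Nothing in the model represents a person's slope or curvature varying from one session to the next, whether by carry-over within a session or by real change.

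At stake are c(iii), curves that climb less steeply with each session, and c(iv), an earlier turning point. Each is decided on one p-value from this model. A change in curve shape over sessions could be declared when there is none.

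**Working it through.** **The plan's own figure.** The 50 participants for analysis d cannot be reproduced. The SAP gives no effect size, residual variance, random-effect variances, correlation or significance level for it. The check below therefore concerns the type I error.

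**Inputs from the SAP (section 3, analysis d).** 3 sessions, 20 rises, session as a linear score, centred rise, random curve per participant only.

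**Assumptions.** Two-sided nominal 5%; complete data; no true session effect on curve shape; residual variance 1; within-session residual correlation ρ^|i−j| between rises i and j (AR(1)), independent between sessions.

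**Step 1: true variance.** Let p₀, p₁, p₂ be the orthonormal constant, linear and quadratic contrasts over the 20 rises and R the AR(1) matrix. Each session's coefficient has residual variance q_k = p_k′Rp_k. The participant's curve cancels from the session-linear contrast, so q₁ governs sess:rise and q₂ governs sess:rise^2.

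**Step 2: variance the model uses.** Each participant has 60 ratings, less 3 degrees of freedom for the participant's curve, so the expected residual variance is s² = [60 − (q₀ + q₁ + q₂)]/57.

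**Step 3: actual error.** With k = q/s², the rejection rate is 2 × [1 − Φ(1.96/√k)]. True and model variance both scale as 1/N, so k does not depend on N.

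**Example, ρ = 0.5.** q₀ = 2.800, q₁ = 2.412, q₂ = 2.057. s² = (60 − 7.269)/57 = 0.925. For sess:rise, k = 2.412/0.925 = 2.61, giving 22.5%. For sess:rise^2, k = 2.057/0.925 = 2.22, giving 18.9%.

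| ρ | k, sess:rise | error | k, sess:rise^2 | error |
|---|---|---|---|---|
| 0 | 1.00 | 5.0% | 1.00 | 5.0% |
| 0.1 | 1.20 | 7.3% | 1.17 | 7.0% |
| 0.2 | 1.44 | 10.2% | 1.37 | 9.5% |
| 0.3 | 1.74 | 13.7% | 1.61 | 12.3% |
| 0.5 | 2.61 | 22.5% | 2.22 | 18.9% |
| 0.7 | 4.08 | 33.2% | 2.89 | 24.9% |

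**Check by simulation** (4,000 trials per cell). At ρ = 0.5 the rates were 23.8% / 18.5% with N = 50 and 22.1% / 19.1% with N = 100. Full mixed-model fits of model d (N = 50, ρ = 0.5, 400 fits) gave 21.0% / 17.3%.

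**Weaker carry-over.** If half the residual variance is white noise and the other half is AR(1), R becomes 0.5R + 0.5I. The rates fall to 9.3% / 8.6% at ρ = 0.3 and 14.1% / 12.0% at ρ = 0.5.

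**Candidate remedies.**

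- *Random intercept per person and session only:* 14% / 13%, 24% / 21% and 38% / 29% at ρ = 0.3, 0.5 and 0.7. It does not help, because it models level and not shape.
- *Per-person session trend in the linear and quadratic coefficients, tested across persons:* 4.2% to 5.7% for ρ from 0 to 0.7 and N = 50, 92 and 100.
- *AR(1) residual alone:* 3.9% to 6.1% when the residual truly is AR(1). With ρ = 0 but true session-to-session variation in curves (intercept SD 0.5, slope SD 0.5 per SD of rise, curvature SD 0.3, residual SD 1; N = 50, 1,000 trials, balanced approximation), sess:rise rejected in 15.4%.

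**The case against.** **The size rests on a figure that the plan does not give.** The relevant correlation is what remains after each person's own intercept, slope and quadratic are removed. The SAP offers no value for it, and no rating scale or spacing of rises from which to judge one. At ρ = 0.05 the error is only about 6% for each test. This stands. A reader might infer that c(iii) and c(iv) will reject far more often than 5%, but the document does not support that as a fact. It supports a conditional statement: modest for weak carry-over, two to three times nominal at ρ of 0.2 to 0.3, and more beyond that.

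**Pure AR(1) is the strong form of the assumption.** Ratings also contain noise that does not carry over, and the half-noise case shows a clear reduction. This stands too. The 33% / 25% row is the far end of the range.

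**Serial correlation may not be the root of it.** Real change in a person's curve between sessions would inflate the same two tests with no serial correlation at all. This is correct. The underlying gap is the missing person-by-session error term for slope and curvature, and carry-over is one route to it. If that missing term is also raised elsewhere, it is the same point and should be counted once.

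**The reach is limited.** A reader might infer that the experimental-versus-control results are compromised. They are not affected by this point. c(iii) and c(iv) pool both groups and contain no group term; c(v) and d(iii) are between-person tests; the HIQ hypotheses use other models.

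None of these objections supplies the missing error term. The model and its test are written out in full, and nothing elsewhere in the document repairs it.

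**Conclusion.** The point holds in conditional form. As specified, the standard errors for c(iii) and c(iv) are valid only if ratings are independent given one curve per person that does not change shape between sessions beyond the fixed session effects. With positive carry-over, the actual error exceeds the nominal level by an amount that depends on ρ and on the share of non-carrying noise, and a larger sample does not reduce it. Both the 5% level and every value of ρ are assumptions. The direction follows from the stated model, but the size cannot be fixed from the SAP. The change should be made, since two hypotheses rest on these tests alone; confidence in the practical size is medium.

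**What to change.** Base c(iii) and c(iv) on person-by-session curves as the error term, in one of two ways:

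1. Add `(rise + rise^2 | id:sess)` to model d.
2. Estimate each person's linear and quadratic coefficient per session and test their session trend across persons. This is the version that was simulated; the first is its mixed-model counterpart.

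An AR(1) residual within person and session may be added, or reported as a sensitivity analysis. It should not be the sole remedy, because it does not cover real session-to-session differences in curve shape. State the significance level at the same time.

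The cost is SAP wording and a changed fit, with no new data. Section 1 of the SAP says that no data had been collected, so at that stage the change could be fixed in advance. The downside is wider intervals for c(iii) and c(iv). The 50 participants stated for 80% power in analysis d should be recalculated and restated under the new error structure, with the assumed variances and correlation shown.
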